## 4.3 Recruitment

Potential study participants will be recruited from an ATN online survey focused on YMSM's willingness to participate in biomedical trials. Briefly, this online survey is recruiting 500 cisgender men ages 15 to 24 who report same-sex attractions and behaviors and who live in the greater Baltimore Metropolitan Area. Once consented online, participants complete a series of domains including demographics (such as race/ethnicity, income, and education level), general mood, overall health, and sexual health behaviors. After completing the survey, participants are asked whether they would like to be contacted to learn more about future HIV prevention trials. Only those who agree to be recontacted will be screened for eligibility into a Phase I HIV prevention biomedical trial. The Hopkins site staff will contact potential participants and invite them to an inperson screening visit. We foresee needing to screen about 48 YMSM to yield an enrollment of 16 YMSM who have consented, are eligible and able to complete the study visits of our Phase I clinical trial.

We will make every effort to ensure that we carryover the diversity of our sample for the biomedical trial. For example, site staff will prioritize the outreach to racial/ethnic minority YMSM when they call to schedule the initial in-person visit. We expect that, at a minimum, a third of the sample screening in-person at the initial

site visit will identify as a racial/ethnic minority. By prioritizing the scheduling for racial/ethnic minority YMSM, we will be able to medical screen a larger proportion of racial/ethnic minority YMSM. Addressing structural challenges keeping YMSM from participating in a biomedical trial. We also recognize that racial/ethnic minority YMSM in Baltimore may also be more likely to experience greater socioeconomical barriers to study participation. To facilitate YMSM's ability to circumvent challenges to participating in the biomedical trial, we also have created financial support systems to offset structural barriers (e.g., paying for transportation, meals and an overnight stay). This is crucial as we recognize that racial/ethnic YMSM may require more time to successfully enroll in the DREAM Phase I trial (e.g., require time to re-screen if treated for STIs given the greater HIV/STI incidence in the community).

## 4.4 Retention

Once participants enroll in this study, the study site will make every effort to retain them for the duration of follow-up in order to minimize possible bias associated with loss-to-follow-up. A retention rate of 90% will be targeted. The study staff is responsible for developing and implementing local standard operating procedures to target this goal. Components of such procedures include:

- Thorough explanation of the study visit schedule and procedural requirements during the informed consent process, and re-emphasis at each study visit
- Thorough explanation of the importance and inter-relatedness of all the product dose and sampling phases to the overall success of the study
- Use of appropriate and timely visit reminder mechanisms (via email and/or telephone/text)
- Immediate and multifaceted follow-up (i.e. phone/text, email, and/or any other communication methods available at the disposal of site's study staff) on missed visits
- The protocol principal investigator in consultation with the site investigator will determine if research participants who fail to complete all biopsy collection sessions should be replaced. Replacement subjects would be assigned the same sampling schedule as the subject they are replacing.
- Any participant with quantifiable plasma TFV/FTC or peripheral blood mononuclear (PBMC) TFV-DP/FTC-TP concentrations at the Enrollment Visit (Visit 2) will be replaced. Participants with quantifiable plasma tenofovir/emtricitabine concentrations at Visit 2 will not proceed to the tenofovir douche administration and pharmacokinetic sampling portion of the protocol. PBMC TFV-DP/FTC-TP concentrations will be measured periodically. Participants with quantifiable TFV/DP/FTC-TP concentrations may continue to the TFV douche administration and pharmacokinectic sampling portion of the protocol, but may be replaced once the PBMC TFV-DP/FTC-TP results are available.

### 4.5 Co-enrollment guidelines

As indicated in Section 4.2, participants must not take part in other research studies involving drugs, medical devices, genital or rectal products, or vaccines after the Screening Visit and while taking part in ATN DREAM unless approved by the Safety and Monitoring Committee (SMC). Should any participant report concurrent participation in contraindicated studies after enrolling in ATN DREAM, the IoR/designee will consult the SMC regarding potential safety considerations associated with co-enrollment.

# 5. STUDY PRODUCT

### **Tenofovir Enemas in JHU Research Unit**

The tenofovir douche will contain TFV 660 mg in 125 mL hypo-osmolar solution at half the osmolarity of iso-osmolar solution. The compounded formulations will be placed in commercially available 125 mL enema bottles. The enema bottles to be used are intended for single-use only and are disposable.

### 5.1 Administration

Each research unit dose of the study product will be administered by a study site investigator or a designated sub-investigator. After douche dosing, research participants will be instructed to retain the fluid without defecation for five minutes, if possible. Five minutes following douche administration by study staff, research participants will be instructed to expel the douche contents. The time of the douche expulsion will be recorded. The douche effluent will be collected and volume measured so that a single 1 mL sample of this effluent may be assessed for TFV concentration. The results will be volume and dose-corrected (based on administered dose) to establish the % retention of the enema volume post-expulsion. Any deviations or occurrences of note during product administration will be noted in the participant study record.

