### **5.4 Study Product Dispensing**

Study products will be dispensed from the pharmacy to the designated study staff for an enrolled participant only upon receipt of a written prescription from an authorized prescriber as noted on the FDA 1572 form. Pre-procedural cleansing enemas will be administered by study participants. Study product enemas will be administered to subjects by study staff, in order to ensure maximal retention of study product in the desired anatomic compartment, and maximum comparability.

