# Table 9: Visit 2 – Enrollment Visit

### 6.5 Visit 3 - Dosing Visit (Day 1)

Visit 3 must take place > 7 days and  $\leq$ 21 days after Visit 2 (the Enrollment Visit) and  $\leq$ 45 days from the Screening Visit 1. Prior to using the TFV douche, baseline samples (see Appendix 1) will be collected to establish pre-dose conditions for safety assessments as well as sample collection for TFV analyte concentration in multiple matrices for participants taking oral TDF/FTC PrEP. These concentrations will be used to adjust post-dose PK and PD assessments.

YMSM will then receive a dose of the TFV douche at the research unit, and, asked to retain the douche without defecation for 5 minutes, if possible. Subsequently, participants will be instructed on how to expel the douche contents. The amount of time that the douche was retained and the volume of expelled effluent will be measured. Post-dose observations and data collection will follow at 1, 6, 24 and 72 hours, using a sparse sampling design in which paired plasma and peripheral blood mononuclear cells (PBMC) are collected at all PK sampling times.

Participants are assigned to a single time point for flexible sigmoidoscopy with rectal biopsies at either 1,6, 24, or 72 hours after dosing (thus, providing 4 subjects at each time point). Anoscopy, with rectal fluid collection will occur pre-dose and at either 1, 6, 24, or 72 hours after dosing, coinciding with each participant's flexible sigmoidoscopy. Microbiome specimens will be collected via anoscopy pre-dose and at 24 hrs post-dose.

Between sampling windows, YMSM will complete a web-survey examining their perceived reactions and comfort using the study douche, factors influencing product use in the future, and comfort with the trial procedures. The survey will be administered after dosing, but scheduled not to interfere with other study assessments. Sampling for safety, PK, PD, and acceptability assessments will be collected according to a schedule of events (see Appendix 1). A summary of the proposed activities to take place at this visit is noted below:

Component	Procedure/Analysis
	Confirm participant understood and signed informed consent
	Review/update locator information
	Confirm eligibility
Administrative	• Ensure participant complied with pre-visit instructions
Aummistrative	
 
Provide counseling and condoms:
 

	
 
HIV/STI risk reduction counseling
 

	• Provide a copy of pre- and post- visit reminders

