	• Participant education: flexible sigmoidoscopy procedure with biopsy (for participants assigned
	to 24 hr sampling) & rectal fluid collections
	Review/update medical history
	Review/update concomitant medications
Clinical	• Review any available test results
Chincar	• Perform symptom-directed physical exam, including rectal exam, as needed
	• Complete AE assessment
	• Collect vital signs (HR, BP, temp)
	Collect blood specimens for
	• CBC with differential
Safety Labs: blood	o CMP
	• HIV-1 antigen/antibody 4 th generation testing (confirmatory tests as needed)
	If indicated, syphilis (confirmatory tests as needed)
Safety Labs  : urine	• Collect urine sample for GC/CT (NAAT), if indicated
and rectal	• Collect rectal swab for GC/CT (NAAT), if indicated
	• Collect swab for HSV, if indicated
Study Product	Investigator or designated sub-investigator will administer study product to participants
Administration	
Blood for PK,	• Pre-Dose (within 30 min prior to dosing)
plasma, and PBMC	• Post-Dose:**
	$\circ$ 1 hr $\pm$ 15 min
Rectal Specimens:	$\circ$ 6 hr $\pm$ 60 min
Douche effluent	Collected to measure volume and TFV/FTC concentration
Rectal Specimens:	COVID-19 sigmoidoscopy pre-screening per institutional policy
Biopsies for PK/PD,	
histology	• Perform flexible sigmoidoscopy with biopsy collection at 1 hr ± 40 min, or 6 hr ± 40 min post-dose per each participant's designated specimen collection schedule **
(age 18 and above	per caen participant s'uesignated specifien concetion senedule
only)	
Rectal Specimens: Rectal Fluid for PK	Collect rectal swab for microbiome assessment
(Not conducted in	• Collect rectal fluid pre-dose for all participants and at 1 hr (± 15 min) or 6 hr (± 60 min) post-
participants < age 18;	dose per each participant's designated specimen collection schedule**
Prioritized for	
participants age 18	
and above)	
and Microbiome	
(collected in all	
participants)***	
Behavioral	Participant will complete Research Unit Dose Acceptability Questionnaire

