## 9. STATISTICAL CONSIDERATIONS

#### 9.1 Overview and Summary of Design

This is an exploratory, open label study to compare the safety, PK, PD, and acceptability of the formulation of a TFV microbicide enema. The goal of the study is to describe the pharmacokinetic parameters in a population of a TFV douche currently under development in a population of young men who have sex with men (YMSM).

Eligible YMSM will be contacted by site staff to schedule an in-person Screening Visit at the ATN site. A Screening Visit will take place up to 45 days prior to the Baseline enrollment Visit. At this visit, YMSM ( $n\approx48$ ) will learn about the Phase I trial and be invited to participate in the study. All participants will be consented and those who agree to participate in the Phase 1 portion the study will complete Screening Procedures, which includes a medical exam, HIV/STI testing, and a brief, online survey regarding their sexual behaviors, prior experiences and comfort using rectal products, experiences and willingness to participate in the trial and scheduled for their PK/PD visit once all HIV/STI labs have been confirmed. YMSM who choose not to participate in the Phase I trial or who are ineligible to participate due to labs results ( $n\approx32$ ) will be invited to participate in an online-facilitated in-depth interview (IDI). The screening, enrollment, dosing, and termination visits will take place at Johns Hopkins University.

After completing the screening evaluation, we will enroll 16 evaluable participants. YMSM who are willing and cleared to participate in the Trial visit will be asked to use a single dose of a tenofovir (TFV) rectal microbicide douche (600mg TFV in 125mL 0.45% NaCl [half-normal saline]) at the Hopkins study site. Prior to using the TFV douche, baseline samples (see Appendix 1) will be collected to establish pre-dose conditions for safety assessments.

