Pharmacokinetics: To characterize the systemic and compartmental pharmacokinetics of a TFV douche following rectal application, as measured by TFV concentrations in plasma, rectal fluid and rectal mucosal tissue homogenates and cells. Pharmacokinetic parameters will be compared to data from studies using rectal dosing of TFV in DREAM-01 and other oral TFV dosing studies in adults, which also included colorectal biopsies. Pharmacokinetics in blood plasma and PBMCs, colon tissue homogenate and cells, and rectal fluid for the TFV-based douche will be evaluated after rectal administration. The primary analysis will use noncompartmental methods to estimate pharmacokinetic parameters, including peak concentration (Cmax, time to peak concentration ( $T_{max}$ ), area under the matrix concentration-time curve from 0 to infinity ( $0 \rightarrow \infty$ ), and terminal elimination half-life. For sparsely sampled matrices (colon tissue homogenate, colon tissue cells, and rectal fluid), we will use population PK methods to build PK models describing individual PK parameter estimates and typical values for the population along with significant covariates (possibly weight, age, pharmacogenetics, creatinine clearance). Tenfovir and TFV-DP assays will be performed by the Clinical Pharmacology Analytical Laboratory (CPAL) at Hopkins and are validated following FDA bioanalytical guidance and approved by an NIH-cross network Clinical Pharmacology Quality Assurance (CPQA) program before used in clinical studies. Primary PK analyses will be testing for (1) differences in PK measures between the two age groups (Kruskal-Wallis) and (2) comparison with DREAM-01 PK results.

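### The effluent calculation in section 5.1 gives percent of TFV dose retained, not percent of enema volume, and section 9.6 uses neither retained dose nor retention time in any PK analysis

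*Combined protocol and SAP*

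**What the plan says.** **Measurement.** Section 5.1 has staff give the douche and asks participants to hold it for five minutes where they can. The effluent is then collected and its "volume measured so that a single 1 mL sample of this effluent may be assessed for TFV concentration". Section 6.5 adds: "The amount of time that the douche was retained and the volume of expelled effluent will be measured". The effluent row of Table 10 reads "Collected to measure volume and TFV/FTC concentration", and section 6.14.2 lists the same assay among the research laboratory tests, to be run as indicated.

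**Derived quantity.** Section 5.1 continues: "The results will be volume and dose-corrected (based on administered dose) to establish the % retention of the enema volume post-expulsion".

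**Dose.** Section 5 states: "The tenofovir douche will contain TFV 660 mg in 125 mL hypo-osmolar solution". Sections 1.3, 3, 5.2 and 7.6.3 agree with it. Section 9.1 gives "600mg TFV in 125mL 0.45% NaCl [half-normal saline", as does the study summary at the front.

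**Analysis.** Neither retained dose nor retention time appears among the objectives and endpoints in section 2. In section 9.6 the population PK model is to look for "significant covariates (possibly weight, age, pharmacogenetics, creatinine clearance" and similar. The primary PK tests are Kruskal-Wallis between the two age groups and a comparison with DREAM-01, with no adjustment stated.

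**Relevance of retention.** Section 5.4 says that staff administer the product "in order to ensure maximal retention of study product in the desired anatomic compartment, and maximum comparability".

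**The concern.** Two different quantities share one name. An analyst following section 5.1 would compute a drug fraction and report it as a volume fraction. Another, reading only the label, would compute it from volume. The product is hypotonic (about 145 mOsm/kg, section 1.3), so an unchanged concentration during retention cannot be taken for granted.

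The second part concerns use. Sections 1.1 and 1.6 say that behaviour, rather than biology, is the reason for extending the work to young people, and section 1.6 wants a PK bridge from adults. How long a participant holds the fluid, and how much he expels, is one route by which behaviour could alter the delivered dose. If exposure differs between ages 15-19 and 20-24, section 9.6 has no step that would tell a difference in delivered dose from a difference in disposition, although the data needed are collected on the dosing day.

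**Working it through.** **The plan's own figures.** The plan gives no figure for retention or its variability, so there is none to reproduce. The nearest stated figure is in section 9.4: 80% power at 1.0 SD, two-sided 5%, for 8 participants against DREAM-01 (18 adults). For 8 versus 18 I get 62% (noncentral t) or 65% (normal approximation). About 80% appears with 16 versus 18 (80.6%, t). That is a separate matter, and this point does not rest on it.

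**Formulas.** Let V and C be effluent volume and TFV concentration, V0 = 125 mL and D the administered dose.

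- Volume retained = 1 - V/V0
- Drug retained = 1 - (C x V)/D
- With C0 = D/V0, drug retained = 1 - (C/C0) x (V/V0), so the two are equal only when C = C0.

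**Illustrations.** These use D = 660 mg and C0 = 660/125 = 5.28 mg/mL, the values in Table 2. This is not a view on which dose passage is right. The effluent values are assumed.

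| V (mL) | C (mg/mL) | C x V (mg) | Volume retained | Drug retained |
|---|---|---|---|---|
| 80 | 5.28 | 422.4 | 36% | 36% |
| 80 | 6.6 | 528 | 36% | 20% |
| 100 | 4.0 | 400 | 20% | 39.4% |
| 125 | 4.0 | 500 | 0% | 24.2% |
| 130 | 4.5 | 585 | -4% | 11.4% |

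The gap can run either way: the second row assumes that water leaves faster than drug, the last three that the effluent is diluted or drug leaves faster. The documents support neither direction.

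**Denominator.** For 500 mg expelled:

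- 660 mg given: 1 - 500/660 = 24.2% retained
- 600 mg given: 1 - 500/600 = 16.7%
- 120 mL given at 5.28 mg/mL (633.6 mg): 1 - 500/633.6 = 21.1%. Section 12.3.1 describes the administered volume as about 120 to 125 mL.

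**What adjustment might gain.** Let R2 be the share of between-participant variance explained by retained dose. This is an assumption; no document gives it. A 1.0 SD difference becomes 1/sqrt(1 - R2) residual SDs. For 8 versus 8 (the age groups in section 9.4), two-sided 5%, t-based and ignoring the degree of freedom spent on the covariate:

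| R2 | Difference in residual SDs | Power |
|---|---|---|
| 0 | 1.000 | 46.1% |
| 0.10 | 1.054 | 50.1% |
| 0.25 | 1.155 | 57.5% |
| 0.50 | 1.414 | 74.9% |

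Retained dose would need to explain about 56% of the variance to reach 80%. The t calculation only approximates the planned rank test.

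**The case against.** The best reply is that this is one wrong word. Effluent volume is measured directly, so percent of volume is available without the assay, and the correction described already implies the drug-retention formula. Staff administration and a common five-minute instruction limit variation. If retention does differ by age, it is part of the exposure difference that a product bridge should show, so the unadjusted comparison is the right main result. Section 1.7 itself warns that the sample may be too small for robust mixed-effects estimates.

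Most of this stands, and it rules out several stronger readings that a reader might infer:

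- **That retention data are lost.** They are not; both percentages can be computed.
- **That the effluent may go unassayed.** Section 5.1 is permissive, but Table 10 and section 6.14.2 plan the assay. The wording needs aligning.
- **That retained dose is excluded as a covariate.** The list in section 9.6 is tentative; retained dose is unnamed, not ruled out.
- **That pharmacogenetics should give way to it.** No dedicated sample is scheduled, but blood cells are collected and specimens stored (section 6.16). Nothing here requires removing that covariate.
- **That ignoring retention costs a known amount of sample size.** Any such figure rests on assumed SDs.
- **That the DREAM-01 comparison can be adjusted in the same way.** Section 1.6 lists blood, rectal fluid and tissue sampling for that study, with no mention of effluent or retention time.

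The reply does not remove the mislabelled definition, or the absence of any stated use for a measurement that section 5.4 links to comparability.

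**Conclusion.** The point holds in a limited form. The calculation in section 5.1 yields percent of TFV dose retained and is named percent of enema volume. The mass-balance identity shows this without any assumption; how far the two differ depends on effluent concentrations that the documents do not give (36% against 20% in one assumed case). The unreconciled dose moves the result further (24.2% against 16.7% for 500 mg expelled).

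Retained dose and retention time enter no endpoint or PK analysis, so an age-group difference in exposure could not be attributed to delivered dose or to disposition. The unadjusted comparison remains valid for bridging; what is missing is a supportive analysis beside it. Its gain in precision cannot be sized from the documents.

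**What to change.** **Section 5.1.** Define percent of TFV dose retained = 1 - (effluent TFV concentration x effluent volume)/administered dose. Report percent of volume retained separately, from the measured volumes. State that every effluent is assayed, in line with Table 10. Reconcile the 600 mg passages (front summary, section 9.1) with the 660 mg passages (sections 1.3, 3, 5, 5.2, 7.6.3), because the dose is the denominator.

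**Section 9.6.** Summarise retained dose and retention time by age group. Add log retained dose as a candidate population PK covariate, with a rule for values at or below zero. Report a supportive age-group comparison adjusted for retained dose beside the unadjusted one, which stays primary. Do the same against DREAM-01 only if that study has effluent data.

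**Cost.** Wording and one supportive model on data already planned. The effluent row in Table 10 carries no age limit, so plasma and PBMC comparisons can use it in all dosed participants; tissue comparisons cannot include those under 18, who have no biopsies. Adjustment removes any age effect that acts through retention, and it will be imprecise at 8 versus 8. Incomplete collection counts as retained drug, so the covariate carries measurement error.

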## **5.2 Study Product**

Tenofovir (PMPA,9-[(R)-2-(phosphonomethoxy)propyl] adenine monohydrate) is a nucleotide analogue belonging to the class of acyclic phosphonomethylether nucleotides with potent activity against retroviruses. Study product should be stored at room temperature 25°C (77°F). After the pharmacist has prepared 150 mL of the enema solution, 20-25 mL of the solution will be placed in a container and sent to the University of Pittsburgh/Magee Women's Research Institute for tenofovir identity/assay, osmolality and pH testing.

The ATN Dream Product contains TFV 660 mg in 125 mL hypo-osmolar solution at half the osmolarity of isoosmolar solution. This study product will be administered in the research unit at Visit 3.

